Approximately 302 subjects will be randomized in a 1:1 ratio to receive either daratumumab + pomalidomide + dexamethasone (DaraPomDex) or pomalidomide + dexamethasone (PomDex). Subjects who already began treatment with Dara IV prior to Amendment 1 will have the option to switch to subcutaneous administration of daratumumab for the remainder of their participation in the study and they will be counted toward the total of 302 subjects. Treatment cycles have a duration of 28 days. Subjects will receive treatment until disease progression or unacceptable toxicity. Drug administration and follow-up visits will occur more frequently for early cycles (eg, weekly or bi-weekly).

Assessment of myeloma response and disease progression will be conducted in accordance with the modified International Myeloma Working Group (IMWG) response criteria. Disease evaluations will occur monthly and consist primarily of measurements of myeloma proteins. Other measures may include bone marrow examinations, skeletal surveys, assessment of extramedullary plasmacytomas, and measurements of serum calcium corrected for albumin. Survival status, subsequent anti-myeloma treatment data, and patient reported outcome (PRO) measures will continue to be collected post-treatment.

Objectives: The primary objective of this study is to compare progression free survival (PFS) between treatment arms.

The secondary objectives are the following:

- To compare Overall Response Rates (ORR) between treatment arms
- To compare Duration of Response (DoR) between treatment arms
- To compare time to next therapy between treatment arms

- To compare Overall Survival (OS) between treatment arms
- To assess the safety and tolerability of the investigational combination treatment
- To assess the depth of response by analysis of minimal residual disease (MRD) rate for subjects with complete response (CR/sCR) and for subjects with suspected CR/sCR
- To compare health-related quality of life (HRQoL) and health utility between treatment arms
- To evaluate the immunomodulatory effects of daratumumab on T cells
- To evaluate daratumumab pharmacokinetics and immunogenicity and the immunogenicity of rHuPH20

Endpoints:

Primary endpoint: Progression free survival

Secondary Endpoints:

- ORR
- Very good partial response (VGPR) or better rate
- CR or better rate
- MRD negativity rate
- Time to response
- DoR
- Time to next therapy
- OS
- Safety (adverse events)

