3.2 SECONDARY OBJECTIVES

The secondary objectives of the study are the following:

- To compare ORRs between treatment arms.
- To compare DoR between treatment arms.
- To compare time to next therapy between treatment arms.
- To compare OS between treatment arms.
- To assess the safety and tolerability of the investigational combination treatment.
- To assess the depth of response by analyzing MRD negativity rate for CR or better and for suspected CR/sCR.
- To compare health-related quality-of-life (HRQoL) and health utility between treatment arms.
- To evaluate the immunomodulatory effects of daratumumab on T cells.
- To evaluate daratumumab pharmacokinetics and immunogenicity and the immunogenicity of rHuPH20.

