Drug administration and follow-up visits will occur more frequently for early cycles (eg, weekly or bi-weekly) (see [Table 7.3](#)). Disease evaluations will occur every cycle and consist mainly of measurements of myeloma proteins. Other parameters may include bone marrow examinations, skeletal surveys, assessment of extramedullary plasmacytomas, and measurements of serum calcium corrected for albumin. Patient reported outcome measures will be administered on Day 1 of each treatment cycle, prior to receiving treatment or any other assessment. The schedule of assessments will be adjusted for subjects remaining on study after the positive primary analysis and is detailed in [Section 7.2.4](#). A schedule of assessments is provided in [Appendix 12](#) (and detailed in [Table 7.3](#)) for subjects continuing on study treatment after the CCO for the final OS analysis.

Assessment of myeloma response and disease progression will be conducted in accordance with the modified IMWG response criteria.

Survival status, subsequent anti-myeloma treatment data, and PRO measures will continue to be collected post-treatment.

The primary analysis of PFS will occur after 188 PFS events have been observed. Long-term survival follow-up and data collection will continue until approximately 166 deaths have been observed or 5 years after the last subject is randomized, whichever occurs earlier. Subjects benefiting from the study treatment can continue to receive study treatment after the CCO for the final OS analysis. For these subjects, study treatment will be available through continued access within the current study until it is available through another source such as commercial availability with reimbursement, continued access through a long-term extension study, a patient access program, or after the last subject transitions into the long-term extension phase of the study up to 30 September 2024, whichever occurs first.

Figure 4.1: Study Design

*The schedule of assessments will be adjusted for subjects remaining on the study after the positive primary analysis and is detailed in *Section 7.2.4*. A schedule of assessments is provided in *Appendix 12* (and detailed in *Table 7.3*) for subjects continuing on study treatment after the CCO for the final OS analysis.

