4.2.2 Secondary Endpoints

- Overall response rate
- VGPR or better
- Complete response (CR) or better
- MRD negativity rate
- Time to response
- Duration of response (DoR)
- Time to next therapy
- Overall survival
- Safety (adverse events)
- Scale and domain scores of the European Organization for Research and Treatment of Cancer Quality of Life Questionnaire Core-30 item (EORTC QLQ-C30) (global health status, physical functioning, emotional functioning, fatigue, pain) and European Organization for Research and Treatment of Cancer Quality of Life Questionnaire Multiple Myeloma Module (EORTC QLQ-MY20) (disease symptoms, side effects of treatment)
- European Quality of Life Five Dimensions Questionnaire (EQ-5D-5L) health utility values
- Immunomodulatory effects of daratumumab on T cells
- Daratumumab pharmacokinetic concentrations (Dara IV and Dara SC)
- Daratumumab and rHuPH20 immunogenicity in subjects who receive Dara SC

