7.1.3 Patient Reported Outcome Measures

Patient-reported outcome measures will be administered on Day 1 of each treatment cycle prior to receiving treatment or any other assessment. Post-treatment, PRO measures will be administered every 4 weeks for subjects who discontinue treatment for reasons other than disease progression, death, lost to follow-up, or withdrawal of consent.

EQ-5D-5L

The EQ-5D-5L is a generic measure of health status. For purposes of this study, the EQ-5D-5L will be used to generate utility scores for use in cost effectiveness analyses. The EQ-5D-5L is a 5-item questionnaire that assesses 5 domains, including: mobility, self-care, usual activities, pain/discomfort, and anxiety/depression plus a visual analog scale rating “health today” with anchors ranging from 0 (worst imaginable health state) to 100 (best imaginable health state) (*Herdman et al 2011*). The scores for the 5 separate questions are categorical and cannot be analyzed as cardinal numbers. However, the scores for the 5 dimensions are used to compute a single utility score ranging from zero (0.0) to 1 (1.0), with higher values representing better general health status of the individual. Administration time for the EQ-5D-5L is less than 10 minutes.

EORTC QLQ-C30

The EORTC QLQ-C30 Item is a cancer-specific PRO measure. It includes 30 items resulting in 5 functional scales (physical functioning, role functioning, emotional functioning, cognitive functioning, and social functioning), 1 Global Health Status scale, 3 symptom scales (fatigue, nausea and vomiting, and pain), and 6 single items (dyspnea, insomnia, appetite loss, constipation, diarrhea, and financial difficulties). Scores are transformed to a 0 to 100 scale. A higher score for the global health status scale represents higher quality of life, a higher score for the functional scales represents higher level of functioning, and a higher score for symptom scales/items represent higher level of symptomatology/problems. Reliability, validity, and clinically meaningful change of the EORTC QLQ-C30 have been demonstrated in MM patients (*Wislöf et al 1996*; *Wislöf & Hjorth 1997*). The recall period is 1 week (the past week), and the questionnaire takes approximately 15 minutes to complete.

EORTC QLQ-MY20

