10.4 DESCRIPTION OF STATISTICAL METHODS

10.4.1 General Approach

All data collected in this study will be listed and summarized as appropriate as described below. Data from all sites will be pooled and summarized.

Continuous data will be summarized by mean, standard deviation (SD), median, first and third quartiles, and minimum and maximum. Categorical data will be presented by absolute and relative frequencies (n and %) or contingency tables.

One-sided alpha level 0.025 will be used for the primary endpoint, PFS. Hierarchical testing of secondary endpoints will be specified in the Statistical Analysis Plan (SAP) to strongly control the family-wise Type I error rate at one-sided alpha of 0.025.

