10.4.3 Analysis of the Secondary Endpoint(s)

All secondary efficacy analyses will be performed based on the ITT analysis set.

Overall Response Rate (ORR)

Overall response rate is defined as the proportion of randomized subjects who achieve a best response of PR or better using modified IMWG criteria ([Appendix 2](#)).

Overall response rate will be compared between arms using a stratified Cochran Mantel-Haenszel (CMH) chi-square test with a two-sided $\alpha = 0.05$ level. The response rate, along with its exact two-sided 95% CI, will be computed within each treatment group. A two-sided 95% CI for difference of response rate between the treatment groups will also be computed.

A sensitivity analysis of ORR may be conducted by excluding those subjects who already began treatment with Dara IV prior to Amendment 1.

Very Good Partial Response (VGPR) or Better Rate, CR or Better Rate, MRD Negativity Rate

Very good partial response (VGPR) or better rate is defined as the proportion of randomized subjects who achieve a best response of VGPR or better using modified IMWG criteria.

Complete response (CR) or better rate is defined as the proportion of randomized subjects who achieve a best response of CR or better using modified IMWG criteria.

Minimal residual disease (MRD) negativity rate is defined as the proportion of randomized subjects who achieve a negative result of MRD. Subjects without MRD assessment will be considered as having MRD-positive results.

These categorical endpoints will be analyzed similarly to ORR.

Time to Response

Time to response is defined for subjects who achieve a confirmed response as the time between the date of randomization and the first efficacy evaluation that the subject has met all criteria for PR or better.

Descriptive statistics will be used to summarize time to response.

Duration of Response (DoR)

Duration of response will be restricted to the randomized subjects who achieve a best response of PR or better. It is measured from the time, in months, that the criteria for response are first met until the date of a progression event (according to the primary definition of PFS). A subject with response who does not have a progression event will be censored at the same time they were censored under the primary definition of PFS.

The DoR for each treatment group will be estimated descriptively using the Kaplan-Meier product-limit method.

Time to Next Therapy

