Time to next therapy will be defined as the time, in months, from the date of randomization to the date of subsequent antimyeloma therapy or death from any cause, whichever comes first. For subjects who neither start a new antimyeloma therapy nor die, survival time will be censored at the date of their last available follow-up date. For a randomized subject who does not have any post-baseline follow-up assessments and who has not died, survival time will be censored at the randomization date.

Time to next therapy will be analyzed similarly to PFS.

Overall Survival (OS)

Overall survival is defined as the time, in months, from the date of randomization to the date of death from any cause. If a subject is not known to have died, survival time will be censored at the date of last contact (“last known date alive”). Overall survival will be analyzed similarly to PFS.

Patient Reported Outcomes Measures

EORTC QLQ-C30, EORTC QLQ-MY20 scale and single-item scores, and EQ-5D-5L visual analog scale and utility values will be summarized at each time point. Treatment effect will be assessed by change from baseline at each time point summarized by treatment group.

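### HRQoL and health utility are to be compared between arms, but the stated PRO analysis only summarizes change from baseline by arm, with no between-arm difference, confidence interval or baseline covariate

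*Combined protocol and SAP*

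**What the plan says.** The objective is comparative. Section 3.2 reads "To compare health-related quality-of-life (HRQoL) and health utility between treatment arms", and the Protocol Summary has the same aim. Section 4.2.2 makes the endpoints specific: five QLQ-C30 scales ("global health status, physical functioning, emotional functioning, fatigue, pain"), two QLQ-MY20 scales (disease symptoms and side effects of treatment) and the EQ-5D-5L utility.

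The analysis is two sentences at the end of Section 10.4.3. Scores are summarized at each time point, and then: "Treatment effect will be assessed by change from baseline at each time point summarized by treatment group". Section 10.4.1 supplies the statistics: "Continuous data will be summarized by mean, standard deviation (SD), median, first and third quartiles, and minimum and maximum".

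Elsewhere Section 10.4.3 does specify contrasts. For ORR it gives a stratified test and adds: "A two-sided 95% CI for difference of response rate between the treatment groups will also be computed". OS and time to next therapy follow the PFS analysis, which has a log-rank test and a hazard ratio with CI (Section 10.4.2).

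Section 10.4.9 limits the alpha-controlled secondary family to OS, ORR, VGPR or better, CR or better and MRD negativity. Sections 10.4.1 and 10.4.8 to 10.4.10 send hierarchical testing, subgroup and additional exploratory analyses to the SAP. None of them sends the PRO analysis there.

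**The concern.** A by-arm summary of change describes each arm. It does not estimate the quantity the objective names, which is the difference between randomized arms, and it does not show how uncertain that difference is. Section 10.4.3 nevertheless presents the summary as the way treatment effect will be assessed.

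A reader could subtract two visit means and build an unadjusted interval from the SDs and counts. A baseline-adjusted difference cannot be recovered from those tables. Section 7.1.3 intends the utilities for cost-effectiveness work, where a between-arm difference and its uncertainty are useful. What is at stake is how the PRO results are read and how precise they are. No type I error claim is involved.

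**Working it through.** **Objective against method.** The plan gives no PRO sample size, SD, effect size or correlation, so there is no PRO figure to reproduce. The core of the point is textual:

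| Item | Objective | Stated analysis |
|---|---|---|
| ORR | Compare arms | Stratified test, CI for the difference |
| OS, time to next therapy | Compare arms | As PFS: log-rank test, hazard ratio with CI |
| DoR | Compare arms | Kaplan-Meier by arm, descriptive |
| HRQoL, utility | Compare arms | Change from baseline by arm, said to assess treatment effect |

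**Precision.** Let B and Y be the baseline and follow-up scores, with common SD s and correlation rho.
- Raw change: Var(Y − B) = 2s²(1 − rho).
- Adjusted for baseline: Var(Y given B) = s²(1 − rho²).
- Ratio, adjusted to raw: (1 + rho)/2.
- For rho = 0.3, 0.5, 0.7 the ratio is 0.65, 0.75, 0.85. The raw CI is wider by 1/√ratio − 1 = 24%, 15%, 8%.

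The 95% half-width at one visit is 1.96 × s × k × √(1/n₁ + 1/n₂), with k = √(2(1 − rho)) for raw change and k = √(1 − rho²) for adjusted. The values below take s = 20 points on the 0-100 scale. Both s and rho are assumptions.

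| Forms (PomDex vs DaraPomDex) | Raw, rho 0.3 / 0.5 / 0.7 | Adjusted |
|---|---|---|
| 151 vs 151 (all randomized) | 5.3 / 4.5 / 3.5 | 4.3 / 3.9 / 3.2 |
| 114 vs 127 | 6.0 / 5.1 / 3.9 | 4.8 / 4.4 / 3.6 |
| 58 vs 83 | 7.9 / 6.7 / 5.2 | 6.4 / 5.8 / 4.8 |

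**Where the lower counts come from.** Section 10.5 gives 151 per arm, exponential PFS and HR 0.621. Cycle 7 Day 1 is 168 days, or 5.52 months, after Cycle 1 Day 1. With S(t) = 0.5^(t/median) for PomDex and S^0.621 for DaraPomDex:
- PomDex median 4.0 months (phase 3 study in Section 2.2): 0.384 vs 0.552, or 58 vs 83 of 151.
- PomDex median 13.8 months (phase 2 study in Section 2.2): 0.758 vs 0.842, or 114 vs 127 of 151.

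These are progression-free counts, used only as a proxy for available forms. Table 7.3 appears to include an end-of-treatment form. Under Section 7.1.3 forms also continue after some treatment stops: "PRO measures will be administered every 4 weeks for subjects who discontinue treatment for reasons other than disease progression" (death, loss to follow-up and withdrawal of consent are also excepted). The counts show that unequal drop-off is possible. They do not show a bias or its direction.

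**Deaths by Cycle 7 Day 1, as a range.** PomDex median OS of 12.7 months (Section 2.2) with HR 0.66 (Section 10.5) gives 0.5^(5.52/12.7) = 0.740 and 0.740^0.66 = 0.820, or 39 vs 27 deaths of 151. If instead 166 deaths in 302 are assumed to accrue exponentially over 60 months, the figure is about 11 per arm. This bears on what a repeated-measures model estimates.

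**The case against.** **DoR is a closer analogue than ORR.** It is also a compare objective, lies outside the alpha-controlled family and is analysed descriptively. The plan may therefore use the verb loosely, and this supports rewording the objective as an acceptable remedy. It does not remove the point. DoR is confined to responders and is openly called descriptive, whereas PROs have a baseline form before treatment in both randomized arms and the text says the summary assesses treatment effect.

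**The SAP may add a model.** It may. Completion tables and rules for missing forms and death are ordinary SAP content, and their absence from the reviewed text does not show that they are unplanned. But the protocol does state a PRO method, and no reviewed passage defers it.

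**Baseline is already handled.** This is partly right: change scores subtract it. What is missing is the baseline score as a covariate.

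**The gain is small.** At 114 vs 127 forms, adjustment narrows the half-width by about 0.3 to 1.2 points. That stands, and it is why the point is modest.

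**Stronger readings that the documents do not support:**
- A reader might see a contradiction between Section 7.1.3 and the general statement in Section 4.1, "Survival status, subsequent anti-myeloma treatment data, and PRO measures will continue to be collected post-treatment". Section 7.1.3 is the operative rule, and the other sentence is a summary that leaves out detail.
- A reader of Section 7.1.1 might infer that treatment stops only after Sponsor-confirmed progression. That text governs how progression is confirmed. Sections 5.3.1, 6.1.6 and 7.2.2 list toxicity and other reasons for stopping.
- A reader might infer that later PRO means are biased in a known direction. Nothing in the documents establishes that.

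**Conclusion.** The point holds as a mismatch between a comparative objective and a descriptive method. The stated PRO analysis provides no between-arm difference, no CI and no baseline covariate. The precision cost of raw change against baseline adjustment is a variance ratio of 0.65 to 0.85. This assumes correlations of 0.3 to 0.7, equal SDs at baseline and follow-up, and a single-visit comparison. In points, at the assumed SD of 20, the half-width falls by about 0.3 to 1.5 across the scenarios shown.

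The primary analysis and the controlled secondary tests are untouched. Drop-off may differ between arms, by an unknown amount and in an unknown direction. This is a cheap improvement and not a threat to the trial's main conclusions.

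**What to change.** Keep the descriptive tables. For the seven QLQ-C30 and QLQ-MY20 scales in Section 4.2.2 and the EQ-5D-5L utility, add a repeated-measures model of change from baseline. Its terms are treatment, visit, treatment-by-visit, baseline score and the two stratification factors of Section 10.6.1 (prior lines and ISS stage). Report the between-arm difference with 95% CI at each scheduled visit, and show the number of forms by arm and visit beside it. Label the results supportive with no alpha claim, and post hoc if the model is added after the 21 July 2020 clinical cutoff given in Table 7.3.

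The cost is modest programming: eight models and one count table, on data already collected. The model assumes data are missing at random. It does not remove drop-off bias, and it treats visits after death as missing, so it is not a while-alive estimate; the text should say so.

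If the sponsor does not want a contrast, the alternative is to reword the objective in the Protocol Summary and Section 3.2 as descriptive, and to stop calling the by-arm summary an assessment of treatment effect.

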10.4.4 Safety Analyses

Safety analyses will be conducted on the safety set and will be reported by actual treatment group.

Adverse Events

Adverse events will be assessed according to the CTCAE (Version 4.03).

The incidence of AEs will be tabulated by Medical Dictionary for Regulatory Activities (MedDRA) System Organ Class (SOC) and Preferred Term (PT). The incidence of AEs will also be summarized by SOC, PT, and severity (based on CTCAE grades).

The same analysis will be repeated for SAEs regardless of drug relationship, for drug-related SAEs, AEs with CTCAE Grade 3 or 4, and for drug-related AEs. AEs for which relationship to study drug is not specified will be considered treatment-related.

Deaths reportable as SAEs will be listed by subject and tabulated by type of AE.

Laboratory Parameters

Categorization of laboratory values will be assigned programmatically as per NCI CTCAE Version 4.03 or according to normal ranges for those parameters without available CTCAE grading. The calculation of CTCAE grades will be purely based on the observed laboratory values, clinical assessments will not be taken into account.

A CTCAE Grade 0 will be assigned for all non-missing values not graded as 1 or higher. Grade 5 will not be used.

For laboratory tests where grades are not defined by CTCAE Version 4.03, results will be graded by the low/normal/high (low and high) classifications based on laboratory normal ranges.

The following by-treatment summaries will be generated separately for hematology, biochemistry, and urinary laboratory tests:

- Worst post-baseline CTCAE grade (regardless of the baseline status). Each subject will be counted only once for the worst grade observed post-baseline.
- Shift tables using CTCAE grades to compare baseline to the worst on-treatment value.
- Shift tables using the low/normal/high/ (low and high) classification to compare baseline to the worst on-treatment value, for laboratory tests where CTCAE grades are not defined.

Listings of all laboratory data with values flagged to show the corresponding CTCAE grades, and the classifications relative to the laboratory normal ranges will also be generated.

Other Safety Data

Electrocardiograms, vital signs, and ECOG PS will be listed and summarized by treatment arm.

ECG

- Shift table baseline to worst on-treatment result
- Listing of ECG evaluations for all subjects with at least 1 abnormality
- Change from baseline QTcF

Vital Signs

- Table with descriptive statistics at baseline, 1 or several post-baseline time points and change from baseline to this/these post-baseline time points

ECOG Performance Status

- Shift tables comparing the baseline PS with the worst post-baseline result

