4 STUDY DESIGN AND ENDPOINTS

4.1 DESCRIPTION OF THE STUDY DESIGN

This is a multicenter, Phase 3, randomized, open-label study comparing daratumumab, pomalidomide and low-dose dexamethasone (DaraPomDex) with pomalidomide and low-dose dexamethasone (PomDex) in subjects with relapsed or refractory MM who have received at least 1 prior treatment regimen with both lenalidomide and a PI and have demonstrated disease progression. The original design of this study was to treat subjects with daratumumab for IV infusion (Dara IV); however, as of Protocol Amendment 1, all new subjects will now be dosed subcutaneously with daratumumab co-formulated with recombinant human hyaluronidase rHuPH20 (Dara SC). Subjects who already began treatment with Dara IV (ie, prior to Amendment 1) will have the option to switch to Dara SC on Day 1 of any cycle starting with Cycle 3 or later. It is to be noted that throughout this document, text was added to highlight any differences between Dara IV and Dara SC dosing; and where there is no clarification, it is implied that the descriptions are the same for both Dara IV and Dara SC.

Approximately 302 subjects will be randomized in a 1:1 ratio to receive either daratumumab + pomalidomide + dexamethasone (DaraPomDex) or pomalidomide + dexamethasone (PomDex). Subjects who already began treatment with Dara IV prior to Amendment 1 will be allowed to switch to subcutaneous administration of daratumumab on Day 1 of any cycle starting with Cycle 3 or later for the remainder of their participation in the study, and they will be counted toward the total of 302 subjects. Treatment cycles have a duration of 28 days.

Pomalidomide will be administered at full dose of 4 mg orally (PO) on Days 1 through 21 of each 28-day cycle.

Daratumumab will be given at a dose of 16 mg/kg administered as an IV infusion (Dara IV) or 1800 mg subcutaneously (Dara SC) at weekly intervals (QW) for 8 weeks, then every 2 weeks (Q2W) for an additional 16 weeks, then every 4 weeks (Q4W) thereafter. Subjects will receive pre-infusion medications before infusions to mitigate potential IRRs.

Dexamethasone will be administered according to standard clinical practice and at a recommended total dose of 40 mg weekly for both treatment groups (20 mg weekly for subjects ≥ 75 years of age).

Subjects will receive treatment until disease progression or unacceptable toxicity.

[figure not shown]

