10.4.6 Treatments (Study Treatment, Concomitant Therapies)

The Safety set will be used for the following analyses.

Investigational Treatment

Duration of study treatment, cumulative dose, average daily dose, actual dose intensity, and relative dose intensity of each of the components of study treatment will be summarized by treatment arm and for every 28-day cycle. The number of subject with dose changes/interruptions will be presented by treatment group, along with the reasons for the dose change/interruptions.

Concomitant Treatments

Concomitant medications or procedures and significant non-drug therapies taken concurrently with the study treatment will be listed and summarized by World Health Organization (WHO) Anatomical Therapeutic Chemical (ATC) Class, PT, and treatment arm. These summaries will include medications starting on or after the start of study treatment (defined as C1D1) or medications starting prior to the start of study treatment and continuing after the start of study treatment. Any prior medication or significant non-drug therapy starting and ending prior to the start of study treatment will be listed.

For the analyses of transfusions, only transfusions received after start of study treatment and up to 30 days after last dose will be considered. The number of subjects with transfusions and number of transfusions per subject will be analyzed.

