10.5 SAMPLE SIZE

Based on the primary endpoint PFS, at a one-sided significance level of 0.025, assuming exponential survival distribution with a HR of 0.621, a total of 280 evaluable subjects (140 per arm) are required to observe 188 events to test the hypothesis with 90% power. Assuming a 7% rate for permanent early censoring before the study cutoff, approximately 302 subjects will need to be randomized (151 per arm).

The primary analysis of PFS will occur after approximately 188 PFS events have been observed. The actual timing of the analysis will depend on the event rates in both control and treatment arms and will be monitored during the study. Long-term survival follow-up will continue until approximately 166 deaths have been observed. Therefore, this study will achieve approximately 70% power to detect a 34% reduction in the risk of death (HR=0.66) with a log-rank test (one-sided alpha=0.025).

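### AEs are summarised only as crude incidence while the AE window lengthens with PFS, so for events that accumulate over time DaraPomDex can look more toxic at equal monthly risk

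*Combined protocol and SAP*

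**What the plan says.** Section 10.4.4 of the protocol (Safety Analyses) states the AE analysis: "The incidence of AEs will be tabulated by Medical Dictionary for Regulatory Activities (MedDRA) System Organ Class (SOC) and Preferred Term (PT"), then by severity, then repeated for SAEs, drug-related SAEs, Grade 3 or 4 AEs and drug-related AEs, by actual treatment group. It gives no person-time denominator, no time-to-first-event or cumulative-incidence method, and no common-window comparison.

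Three other places fix how long each subject is observed:

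- Section 4.1, for both arms: "Subjects will receive treatment until disease progression or unacceptable toxicity".
- Section 7.1.2.1: AE monitoring runs from consent to 30 days after the last study treatment.
- Section 10.5: the design is powered "assuming exponential survival distribution with a HR of 0.621".

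Section 10.4.6 separately summarises "Duration of study treatment, cumulative dose, average daily dose" and dose intensity by arm. These summaries are not used as a denominator for any AE figure.

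**The concern.** The AE window closes 30 days after treatment ends, and treatment normally ends at progression. The arm that delays progression is therefore observed for longer, and a longer window collects more first events even when the risk per month is unchanged. A crude percentage cannot separate added toxicity from added time at risk.

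Assessing the safety and tolerability of the combination is a secondary objective (Section 3.2), and readers will judge added toxicity from the side-by-side percentages. The problem is greatest for events that keep accruing during treatment, such as infections.

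**Working it through.** **1. The plan's own figures.** Inputs from Section 10.5: hazard ratio 0.621; "at a one-sided significance level of 0.025"; "are required to observe 188 events to test the hypothesis with 90% power"; "a total of 280 evaluable subjects (140 per arm"); "Assuming a 7% rate for permanent early censoring before the study cutoff".

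- Events (Schoenfeld): 4 × (1.960 + 1.282)² / (ln 0.621)² = 4 × 10.51 / 0.2270 = 185.2, so 186 against 188 stated.
- Power at 188 events: Φ(√188/2 × 0.4764 − 1.960) = Φ(1.306) = 0.904.
- Sample size: 280/0.93 = 301.1, so 302 in equal arms.

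The design reproduces, so 0.621 and 188 events among 280 subjects (67%) are used below.

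**2. Model and assumptions.** Time on treatment is exponential, with rate λ = ln 2/median in control and 0.621λ on DaraPomDex. AEs have the same constant hazard h per month in both arms. The AE window is treatment time plus w = 30 days (0.986 month), capped at the data cutoff F. The design states no control median, AE hazard or accrual pattern, so ranges are assumed:

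- Control medians of 4.0 to 13.8 months, the two ends of the PomDex background data in Section 2.2.
- h of 0.01 to 0.10 per month.
- Uniform accrual over 0 to 24 months.

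**3. Formulas, for follow-up F.**

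- Mean exposure = (1 − e^(−λF))/λ
- P(AE) = 1 − e^(−hw) + h·e^(−hw)·[1 − e^(−(h+λ)(F−w))]/(h+λ)

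**4. Worked case: median 4.0 months, h = 0.05, instantaneous accrual.** λ = 0.1733 in control and 0.1076 on DaraPomDex. F = 8.18 months gives event fractions of 0.758 and 0.585, mean 0.671 = 188/280.

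- Exposure: 0.758/0.1733 = 4.37 and 0.585/0.1076 = 5.44 months, ratio 1.24.
- Control: 0.0481 + 0.0476 × 0.799/0.2233 = 21.9%.
- DaraPomDex: 0.0481 + 0.0476 × 0.678/0.1576 = 25.3%.
- Crude relative risk: 1.16, with no true difference.

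**5. Over the assumed ranges at the 188-event cutoff.** The exposure ratio is 1.24 to 1.35 and the crude relative risk 1.11 to 1.27. The upper ends come from median 4.0 with 24-month accrual. In that case 188 events would be reached before accrual ends, so the cutoff was set at the end of accrual. The next largest values are 1.30 and 1.23 (median 6.0, 24-month accrual).

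With h chosen to give a set control-arm incidence:

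| PomDex | DaraPomDex, same monthly risk |
|---|---|
| 10% | 12–13% |
| 20% | 23–25% |
| 30% | 34–36% |
| 50% | 56–58% |
| 80% | 84–86% |

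**6. Complete follow-up to progression (upper limit).** The exposure ratio is 1/0.621 = 1.61. The relative risk is 1.13 (median 13.8, h = 0.10) to 1.47 (median 4.0, h = 0.01). The worked case becomes 26% against 35%.

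**7. Events confined to the first two cycles.** 30.0% in control becomes 30.1–30.3% on DaraPomDex, so the artefact is negligible.

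**8. The remedy under the same test.** With a constant equal hazard, the exposure-adjusted rate ratio is 1.00 by construction. With equal risk confined to the first 56 days (about 31–33% crude in both arms), simulation at the cutoff gives a first-event rate ratio of about 0.80 to 0.87. The rate then errs in DaraPomDex's favour.

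**The case against.** A reader might infer that DaraPomDex will look more toxic across the board, with subjects observed about 1.6 times as long. The documents do not support that.

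- **Size.** The 1.61 ratio needs every subject followed to progression, whereas the primary analysis comes at 188 events. The simple formula h/(h+λ) gives relative risks up to 1.56, but it omits both the cutoff and the 30-day window.
- **Timing of toxicity.** Section 2.3.1 says pomalidomide reactions were more frequent in the first two cycles, and the infusion reactions it describes came mostly at the first administration. Very common events have little room to differ: in the earlier DaraPomDex study, Grade 3 or 4 TEAEs affected 99% of subjects.
- **Stopping for toxicity.** Treatment time is not PFS time. TEAEs led to discontinuation in 15% of subjects in that study, and more such stopping on DaraPomDex than on PomDex would narrow the exposure gap.
- **Second primary malignancies.** They are captured every 12 weeks after progression (Section 7.2.4) and followed for 5 years (Table 7.3 notes), so the 30-day window does not govern them.

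All four stand and limit the point. Three further arguments only soften it. The duration summary in Section 10.4.6 shows unequal exposure but corrects no AE figure, and time at risk to first event cannot be recovered from it. The tables are descriptive with no formal test, and crude incidence is a legitimate measure of the chance of an event while on the regimen, but it does not answer whether the combination adds risk per unit of time. Finally, a separate SAP may contain such tables. No separate SAP text is among the documents, and Section 10.4.4 does not defer to one, although Section 10.4.10 leaves exploratory analyses to it. If the SAP has these tables, a cross-reference closes the point.

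**Conclusion.** The point holds for events that accumulate over time: equal monthly risk can appear as a crude excess for DaraPomDex. At the primary cutoff this is modest, with a relative risk of about 1.1 to 1.3 or roughly 2 to 8 percentage points. It moves towards the complete-follow-up values as data mature. That matters for the final report, since collection continues to about 166 deaths or 5 years after the last randomisation (Section 4.1).

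The figures rest on exponential times, treatment time tracking PFS with hazard ratio 0.621, a constant AE hazard, and assumed control medians, hazards and accrual. They do not show that DaraPomDex must look more toxic overall. The primary endpoint, alpha and sample size are unaffected. This is an inexpensive improvement that the sponsor should make.

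**What to change.** Keep the crude tables in Section 10.4.4 and add, by arm:

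- **Exposure-adjusted incidence:** subjects with a first event per 100 patient-years at risk, counting the 30-day window, for Grade 3/4 AEs, SAEs, infections and AEs leading to discontinuation.
- **A common early window:** crude or cumulative incidence over a fixed period such as Cycles 1–6.
- **Second primary malignancies:** events per patient-year of their own follow-up, not of treatment time.

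State in the plan that the first two are to be read together. The person-time rate assumes a roughly constant hazard and can make DaraPomDex look safer for front-loaded events; the early-window table guards against that.

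The cost is a few more tables. AE onset (Section 8.3) and treatment duration (Section 10.4.6) are already collected, so no visit, procedure or endpoint changes.
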